10.1. DERIVATIONS

[figure not shown]
BMI, in kg/m², will be calculated as follows:

- $BMI (kg/m^2) = Weight (kg) / [Height (m)^2]$

11. DISEASE HISTORY

The following disease history endpoints will be summarized overall and by treatment arm based on the FAS. The control arm of a candidate agent (refer to Section 4.5) will be further broken down by sub-protocol.

- Time since onset of first COVID-19 symptom(s) (days) – calculated relative to Study Day 1 (refer to Section

6.1)

- Time since COVID-19 diagnosis (days) – calculated relative to Study Day 1;
- Time since hospital admission (days) – calculated relative to Study Day 1;
- Patients on supplemental oxygen at Study Day 1 (yes or no);
- Type of supplemental oxygen only for patients receiving supplemental oxygen at Study Day 1;
- Time since start of supplemental oxygen (days) - calculated relative to Study Day 1 only for patients on supplemental oxygen at Study Day 1;
- Patients receiving ICU/high dependency unit (HDU)-level care at Study Day 1 (yes or no);
- Time since start of ICU/HDU-level care (days) – calculated relative to Study Day 1 only for patients receiving ICU/HDU-level care at Study Day 1;
- Patients on invasive mechanical ventilation at Study Day 1 (yes or no);
- Type of invasive mechanical ventilation at Study Day 1 only for patients on invasive mechanical ventilation at Study Day 1;
- Time since start of invasive mechanical ventilation (days) – calculated relative to Study Day 1 only for patients on invasive mechanical ventilation at Study Day 1;
- Patients diagnosed with acute respiratory distress syndrome (ARDS; yes or no);
- Time since ARDS diagnosis (days) – calculated related to Study Day 1 only for patients diagnosed with ARDS;
- Patients with or without each of the following COVID-19 symptoms at screening. For each symptom, patients with the symptom will be further broken down by severity (mild, moderate, severe, or unknown):
 - Cough;
 - Fever;
 - Myalgia;
 - Diarrhea;
 - Dyspnea;

CCI [Redacted]

PPD [Redacted]

Version Number: Amendment 1, v1.0
Version Date: 23Apr2021

CCI [Redacted]

[Redacted]

- Fatigue/malaise;
 - Loss of appetite;
 - Loss of smell;
 - Loss of taste.
- Baseline clinical severity score (2, 3, 4, or 5, as well as 2 or 3/4/5) as captured on the *Ordinal Scale for Clinical Severity* page of the eCRF;
 - NEWS2 total score at baseline;
 - Oxygen saturation (SpO₂; %) at baseline;
 - Fraction of Inspired Oxygen (FiO₂; %) at baseline.

All disease history characteristics will be listed.

11.1. DERIVATIONS

Time since events, in days, will be calculated as follows:

- Time since onset of first COVID-19 symptom(s) (days) = (Date of Study Day 1 [refer to Section 6.1] – Date of onset of first COVID-19 symptom[s]); date of onset of COVID-19 symptoms as captured on the *Medical History* page of the eCRF;
- Time since COVID-19 diagnosis (days) = (Date of Study Day 1 - Date of COVID-19 diagnosis); date of COVID-19 diagnosis as captured on the *Medical History* page of the eCRF;
- Time since hospital admission (days) = (Date of Study Day 1 – Date of hospital admission); where date of hospital admission will be the earliest date of hospital admission captured on the *Hospitalization* page of the eCRF;
- Time since start of supplemental oxygen (days) = (Date of Study Day 1 – Date of start of supplemental oxygen) if patient is already on supplemental oxygen at Study Day 1; where the date of start of supplemental oxygen will be earliest date of start of supplemental oxygen as captured on the *Supplemental Oxygen and Mechanical Ventilation* page of the eCRF. That is, time since start of supplemental oxygen will not be computed for patients not on supplemental oxygen at Study Day 1;

CCI

PPD

Version Number: Amendment 1, v1.0
Version Date: 23Apr2021

CCI

- Time since start of ICU/HDU-level care (days) = (Date of Study Day 1 – Date of start of ICU/HDU-level care) if patient is already receiving ICU/HDU-level care at Study Day 1; where the date of start of ICU/HDU-level care will be the earliest date of start of ICU/HDU-level care captured on the *Hospitalization* page of the eCRF; That is, time since start of ICU/HDU-level care will not be computed for patients not receiving ICU/HDU-level care at Study Day 1;
- Time since start of invasive mechanical ventilation (days) = (Date of Study Day 1 – Date of start of invasive mechanical ventilation) if patient is already on invasive mechanical ventilation at Study Day 1; where the date of start of invasive mechanical ventilation will be the earliest date of start of invasive mechanical ventilation captured on the *Supplemental Oxygen and Mechanical Ventilation* page of the eCRF. That is, time since start of invasive mechanical ventilation will not be computed for patients not on invasive mechanical ventilation at Study Day 1.
- Time since ARDS diagnosis (days) = (Date of Study Day 1 – Date of ARDS diagnosis) if patient was diagnosed with ARDS at screening; where the date of start of ARDS diagnosis as captured on the *Medical History* of the eCRF. That is, time since ARDS will not be computed for patients not already diagnosed with ARDS at screening.

12. MEDICAL HISTORY

Medical history is defined as any medical conditions/diseases that started and stopped before screening as well as any medical conditions/diseases that started before screening AND were ongoing at the time of screening.

Medical history will be coded using the Medical Dictionary for Regulatory Activities (MedDRA) version 23.1 or later and will be summarized by System Organ Class and PT overall and by treatment arm based on the FAS. The control arm of a candidate agent (refer to Section 4.5) will be further broken down by sub-protocol. A patient having more than one medical condition/disease within the same System Organ Class or PT will be counted only once for that System Organ Class or PT. In the summary, System Organ Classes will be sorted in alphabetical order and within each System Organ Class, PTs will be sorted in decreasing order of total frequency.

Additionally, for each of the following COVID-19 comorbidities, the number and percentage of patients, as captured on the *Medical History* page of the eCRF, will be reported overall and by treatment arm based on the FAS. The control arm of a candidate agent (refer to Section 4.5) will be further broken down by sub-protocol.

- Any comorbidity, defined as having any of the comorbidities listed below;

CCI

PPD

Version Number: Amendment 1, v1.0
Version Date: 23Apr2021

CCI

- Obesity (refer to Sections 7.7 and 10.1);
- Diabetes;
- Cardiovascular disease;
- Hypertension;
- Chronic lung disease;
- Chronic liver disease;
- Kidney disease;
- Immunosuppressive/immunodeficiency disorder.

13. PRIOR AND CONCOMITANT MEDICATIONS

All medications collected on the *Concomitant Medications* page of the eCRF will be classified as either:

- Prior medications, defined as any medication that started and stopped prior to the date of Study Day 1 (refer to Section 6.1);

or

- Concomitant medications, defined as:
 - Any medication that started before the date of Study Day 1 AND ended on or after the date of Study Day 1, or were ongoing at that time;
 - Any medication that started on or after the date of Study Day 1.

Partially or completely missing medication start and stop dates will be handled as described in [Appendix 1](#).

All medications will be coded using the World Health Organization (WHO) Drug Global dictionary, version September 2020 B3 or later.

Concomitant medications will be summarized by Anatomical Therapeutic Class (ATC) level 2 and preferred drug name overall and by treatment arm based on the FAS. A patient having more than one medication within the same ATC level 2 or preferred drug name will be counted only once for that ATC level 2 or preferred drug name. Further,

CCI

PPD

Version Number: Amendment 1, v1.0
Version Date: 23Apr2021

CCI

CCI [Redacted]

for each sub-protocol, separate summaries will also be presented for patients randomized to the sub-protocol placebo plus SoC treatment group.

[figure not shown]
Additionally, the number and percentages of patients receiving following medications of interest will be summarized overall and by treatment arm based on the FAS. For each sub-protocol, summaries will also be presented for the subset of patients randomized to the Placebo to the candidate agent plus SoC treatment group of the sub-protocol.

- Remdesivir use at baseline (yes or no) based on data collected on the *Concomitant Medications* page of the eCRF (i.e., medications that were being taken by a patient on the day the patient was randomized to a sub-protocol);
- Concomitant use of remdesivir at any time during the period of the analysis being performed (yes or no; refer to Section 7.7);
- Dexamethasone use at baseline (yes or no) based on data collected on the *Concomitant Medications* page of the eCRF (i.e., medications that were being taken by a patient on the day the patient was randomized to a sub-protocol);
- Concomitant use of dexamethasone at any time during the period of the analysis being performed (yes or no; refer to Section 7.7);
- Steroid use at baseline (yes or no) based on data collected on the *Concomitant Medications* page of the eCRF (i.e., medications that were being taken by a patient on the day the patient was randomized to a sub-protocol);
- Concomitant steroid use at any time during the period of the analysis being performed (yes or no; refer to Section 7.7).

All medications (prior and concomitant) will be listed.

14. EXPOSURE TO STUDY DRUG

Each candidate agent included within the study will have a sub-protocol that will provide details of that treatment, including route and mode of administration, dose, dosage regimen, and duration of treatment. The derivations for study drug exposure as well as summaries and analyses of exposure are therefore not covered in this master protocol SAP but will be covered in the SAP for each sub-protocol.

15. COMPLIANCE WITH STUDY DRUG

Similar to study drug exposure, derivations of compliance to study drug as well as summaries and analyses of study drug compliance, are not covered in this master protocol SAP, but will be covered in the SAP for each sub-protocol.

16. EFFICACY ENDPOINTS

Unless otherwise indicated, all efficacy summaries and figures will be presented by treatment arm and visit, when appropriate, based on the FAS. Listings will be provided for all efficacy data.

16.1. PRIMARY EFFICACY

Unless otherwise indicated, all efficacy summaries and analyses will be presented based on the FAS.

16.1.1. TIME TO CONFIRMED CLINICAL RECOVERY THROUGH DAY 29, WITHOUT RE-HOSPITALIZATION THROUGH DAY 29

The primary efficacy endpoint is the time to confirmed clinical recovery through Day 29, i.e., fit for discharge (defined by achieving a score of 6, 7, or 8 on the 8-point ordinal scale for clinical severity), without being re-hospitalized through Day 29.

It is to be noted that:

- The re-hospitalization-free requirement does not apply to patients who achieved an ordinal scale score of 6 that were never discharged from the hospital before Day 29. For such patients, the re-hospitalization-free requirement is superseded by not having a subsequent worsening on the ordinal scale score (i.e., a score < 6 on the ordinal scale for clinical severity) that would remain until Day 29;
- Patients achieving a score of 7 on the ordinal scale for clinical severity discharged to hospice care will be considered as not fit for discharge in the analysis.

The ordinal scale for clinical severity is as follows:

1. Death;
2. Hospitalized, on invasive mechanical ventilation or ECMO;
3. Hospitalized, on non-invasive ventilation or high-flow oxygen devices;

CCI [Redacted]

Master Statistical Analysis Plan

4. Hospitalized, requiring supplemental oxygen;
5. Hospitalized, not requiring supplemental oxygen, requiring ongoing medical care (COVID-19 related or otherwise);
6. Hospitalized, not requiring supplemental oxygen, no longer requires ongoing medical care;
7. Not hospitalized, limitation on activities and/or requiring home oxygen;
8. Not hospitalized, no limitations on activities.

Time to confirmed clinical recovery through Day 29, without re-hospitalization through Day 29, will be measured in days from the date of Study Day 1 (refer to Section 6.1):

- Time to confirmed clinical recovery through Day 29, without re-hospitalization through Day 29 (days) = (Date of event – Date of Study Day) + 1

Refer to Section 6.1 for the definition of Study Day 1.

The following algorithm will be followed to determine if a patient met the event (i.e., confirmed clinical recovery through Day 29, without rehospitalization through Day 29) or should be censored:

1. First, the patient’s alive status by Day 29 will be verified as per data collected on the *Death Details* page of the eCRF. If the patient died before or on Day 29, he/she will be censored at Day 29. If the patient has not died by Day 29, then go to step 2;
2. Second, the patient’s study discontinuation status by Day 29 will be verified as per data collected on the *Disposition* page of the eCRF. If the patient discontinued from the study before or on Day 29, he/she will be censored at date of discontinuation from study. If the patient was still ongoing in the study at Day 29, then go to step 3;
3. Last, it will be verified if a patient had a score of 6, 7 or 8 on the 8-point ordinal scale (as captured on the *Ordinal Scale for Clinical Severity* page of the eCRF) before or on Day 29:
 - a. For patients who had a score of 6 on the 8-point ordinal scale and were never discharged from the hospital before Day 29, it will be checked if patient worsened on the 8-point ordinal scale (i.e., had a score < 6) before or on Day 29:
 - i. If so (i.e., patient worsened) and patient never subsequently re-reached a score of 6 before or on Day 29, the patient will be censored at Day 29;
 - ii. If so (i.e., patient worsened) but patient subsequently re-reached a score of 6 before or on

- Day 29, the patient will be considered as having the event and the date of the event will be the earliest date on which the patient re-reached a score of 6;
- iii. If not (i.e., patient did not worsen), the patient will be considered as having the event and the date of the event will be the earliest date on which the patient had a score of 6 before or on Day 29;
- b. For patients who had a score of 7 on the 8-point ordinal scale, it will first be verified if patient was discharged to hospice care as per data captured on the *Hospitalization* page of the eCRF.
 - i. If so (i.e., patient was discharged to hospice care), the patient will be considered as not fit for discharge and will be censored at Day 29;
 - ii. If not (i.e., patient was discharged, but not to hospice care), then go to step c.
 - c. For patients who had a score of 7 (discharged, but not to hospice care) or 8 on the 8-point ordinal scale, it will be verified if patient was re-hospitalized before or on Day 29 as per data captured on the *Hospitalization* page of the eCRF. To do so, it will be checked if a patient had at least one record where the hospitalization start date is after the earliest date on which the patient had a score of 7 or 8 but before or on Day 29.
 - i. If so (i.e., patient was re-hospitalized), the patient will be censored at Day 29;
 - ii. If not (i.e., patient was not re-hospitalized), the patient will be considered as having the event and the date of the event will be the earliest date on which patient had a score ≥ 6 before or on Day 29;
 - d. Patients who never had a score of 6, 7 or 8 on the 8-point ordinal scale, did not discontinue from the study or died before or on Day 29 will be censored at Day 29

Refer to [Figure 2](#) for a schematic of the primary endpoint determination of date of event and censoring.

[figure not shown]
CCI

PPD

[figure not shown]
Version Number: Amendment 1, v1.0
Version Date: 23Apr2021

CCI

Figure 2 Schematic of Determination of Primary Efficacy Endpoint Date of Event or Censoring

* For patients who had a score of 6, worsened, *re*-reached a score of 6, and were never discharged from the hospital before or on Day 29, earliest date on which the patient *re*-reached a score of 6.

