### **6.3 Measures to Minimize Bias: Randomization and Blinding**

The study will randomize patients on an ongoing basis, in a double-blind manner, to receive either one of the active candidate agents plus SoC or to receive placebo plus SoC. Randomization will be performed using an Interactive Voice/Web Response System (IVRS/IWRS). The system will initially randomize to either an active candidate agent or generically to placebo plus SoC. If a patient is randomized to placebo plus SoC, the system will then further randomize the patient to a specific candidate agent's placebo from within the list of candidate agents available at the site and for which the patient was determined to be eligible. In either of these cases, the blinded team will be aware of the sub-protocol to which the patient has been randomized, but not whether it is the active agent or the agent's matching placebo. The system will limit randomization to those agents (or matching placebo) that are active for randomization, have not reached their total number of planned patients, have been approved by the site, and for which the patient matches the inclusion/exclusion criteria.

If candidate agents are added to and/or dropped from the study, randomization will proceed with an equal probability of assignment to each of the remaining candidate agents, except for situations where a patient does not meet the eligibility criteria for, and hence would be excluded from, one or more of the sub-protocols.

Study treatment will be dispensed at randomization or according to the sub-protocol SoA. Returned study treatment should not be re-dispensed to patients.

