4.5. SELECTION OF THE CONTROL ARM FOR AN ANALYSIS

The subset of the placebo plus SoC group, regardless of which sub-protocol the placebo patient belongs, enrolled concurrently to an active agent with matching inclusion/exclusion criteria will serve as the control arm for the analysis of a candidate agent. An exception to this definition is that if a sub-protocol X is not open at a site for screening, the concurrent placebo from other active sub-protocol(s) at that site will not be eligible for inclusion in the control arm for sub-protocol X. This is because patient’s eligibility for sub-protocol X cannot be determined without sub-protocol consent and obtaining consent for a sub-protocol is not possible until that sub-protocol is opened at a site for screening. It is to be noted that a patient randomized to the placebo arm of sub-protocol X taking the candidate agent of sub-protocol Y for another approved indication (based on data collected on the *Concomitant Medications* page of the eCRF) at the time of randomization will not be eligible for the control arm of the sub-protocol Y.

For each sub-protocol and each site, ‘concurrently’ is defined as the period starting on the date the site was opened

CCI [Redacted]	[Redacted]	Version Number:	Amendment 1, v1.0
PPD [Redacted]	[Redacted]	Version Date:	23Apr2021
CCI [Redacted]	[Redacted]	[Redacted]	[Redacted]
[Redacted]	[Redacted]	[Redacted]	[Redacted]
[Redacted]	[Redacted]	[Redacted]	[Redacted]

for screening for the sub-protocol and ending on the date of the last patient randomized into that sub-protocol for an interim, primary, and final analyses. For IDMC safety analyses, the date of the data cut-off will be used in lieu of the date of the last patient randomized into the sub-protocol.

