5.1. FULL ANALYSIS SET

For each sub-protocol, the full analysis set (FAS) will contain all patients who were randomized to the sub-protocol candidate agent plus SoC arm as well as all patients who were randomized to any placebo plus SoC arm included in the control arm of the candidate agent (refer to Section 4.5).

[figure not shown]
For displays and analyses based on FAS, patients will be classified according to randomized treatment.

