6. GENERAL CONSIDERATIONS

6.1. STUDY DAY

Study day will be calculated from the day of the first dose of the study drug for patients who received at least one dose of study drug and from the day of randomization for randomized patients who were never dosed, and will be used to show start/stop day of assessments and events.

Study day will be computed as follows:

- Study Day = (Date of interest – Date of first dose of study drug/randomization, as appropriate) + 1 if the date of interest is on or after the date of first dose of study drug/randomization, as appropriate;
- Study Day = (Date of interest – Date of first dose of study drug/randomization, as appropriate) if the date of interest is prior to the date of first dose of study drug/randomization, as appropriate.

Based on these formula, Study Day 1 will be the day of the first dose of the study drug for patients who received at least one dose of study drug and the day of randomization for randomized patients who were never dosed.

In the situation where the date of interest is partial or missing, Study Day and any corresponding durations will be considered as missing in the analyses and the date of interest will be presented as partial or missing in the listings.

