14. EXPOSURE TO STUDY DRUG

Patients randomized to sub-protocol COV-01-004

Patients randomized to the apremilast plus SoC or placebo plus SoC treatment groups of COV-01-004 sub-protocol will receive either an apremilast 30 mg or matching placebo tablet, as applicable, twice daily (BID) in a double-blind manner for 14 days or until hospital discharge, death, or discontinuation of study drug, whichever occurs first, in addition to SoC.

Reason for dose modification of study drug (i.e., dose increased, dose reduced, drug interrupted, drug withdrawal, and unknown) will be captured on the *Exposure* page of the electronic Case Report Form (eCRF).

Patients included in the control arm of COV-01-004 sub-protocol who were randomized to the placebo plus SoC group of a sub-protocol other than COV-01-004

It is to be noted that the planned duration of exposure to a study drug, planned frequency of administration of the study drug, and planned route of administration of the study drug will vary from one sub-protocol to the other, but similar information as for COV-01-004 sub-protocol will be captured on the *Exposure* page of the eCRF of these other sub-protocols.

[figure not shown]
CCI [Redacted]

PPD [Redacted]

Version Number: Amendment 1, v1.0
Version Date: 23Apr2021

CCI [Redacted]

[figure not shown]
[Redacted]

Exposure to study drug

The exposure to study drug will be summarized by treatment arm (breaking down the placebo plus SoC arm by sub-protocol) based on the safety analysis set as follows:

- Duration of exposure:
 - Duration of exposure (days) as a continuous variable;
 - Duration of exposure (days) as a categorical variable: 1 to 3, > 3 to 7, > 7 to 14, and > 14;
 - Total number of doses received as a continuous variable, where the total number of doses received is defined as the total number of doses received by each patient, not the total number of doses received across all patients.
- Average dose (mg/day) only for patients randomized to sub-protocol COV-01-004;
- Dose modifications:
 - Number and percentage of patients with at least one dose reduction;
 - Number and percentage of patients with a dose reduction by reason for dose reductions:
 - Adverse events;
 - Due to creatinine clearance < 30 mL/min*;
 - Due to renal replacement therapy*;
 - Other.
 - Total number of dose reductions as a continuous variable, where the total number of dose reductions defined similarly to the total number of doses received;

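### The primary time-to-recovery clock starts at first dose for dosed patients and at randomization for the rest; a between-arm difference in dosing delay would shift the hazard ratio, and a randomization origin would remove that at little cost

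*SAP*

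**What the plan says.** Master SAP 16.1.1 states that the primary time "will be measured in days from the date of Study Day 1", computed as event date minus Study Day 1 date, plus one. Section 6.1 defines the origin in two parts. For dosed patients, "Study day will be calculated from the day of the first dose of the study drug for patients who received at least one dose"; for the others, it runs "from the day of randomization for randomized patients who were never dosed".

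The analysis set is all randomized patients. Section 5.1 adds: "For displays and analyses based on FAS, patients will be classified according to randomized treatment". Section 4.5 builds the control arm from placebo patients "regardless of which sub-protocol the placebo patient belongs, enrolled concurrently to an active agent". Section 14 of the sub-protocol SAPs accepts that the "planned route of administration of the study drug will vary from one sub-protocol to the other": apremilast is an oral tablet, zilucoplan a subcutaneous injection, lanadelumab an infusion.

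The protocol's endpoint definition names no time origin. Its Section 4.1 has dosing begin on Day 1, and the three sub-protocol Schedules of Activities put randomization and first administration in that same column. Protocol 6.3 says: "Study treatment will be dispensed at randomization or according to the sub-protocol SoA". No document sets a maximum interval from randomization to first dose. None of the analyses in Master SAP 16.1.4 or 16.1.5 starts the clock at randomization.

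**The concern.** The groups are formed at randomization, but for nearly every patient the clock starts at a later event. A patient whose recovery date is 14 days after randomization scores 14 + 1 = 15 on a randomization clock. If first dosed one calendar day after randomization, the same patient scores 13 + 1 = 14. The arm dosed later therefore appears to recover sooner, with no difference in outcome.

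In a blinded two-arm trial with one product, delay would be expected to balance. Here part of the control arm receives other products by other routes, so balance is not guaranteed by design. At stake is a shift in the primary hazard ratio and in the error rate of its test. The same origin feeds the futility analyses (16.5.1) and the time-to-death analyses (16.2.5 and 16.4.5).

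**Working it through.** **1. The plan's own figure.** Master SAP 7.1 and 16.5.1 give 490 events, hazard ratio 1.364 (15/11), one-sided alpha 0.025 and 88.3% power. For a fixed design, z = ln(1.364) × √(490/4) − 1.96 = 0.3104 × 11.068 − 1.96 = 1.476, which is 93.0% power. With both futility boundaries enforced (p 0.503 at 123 events, 0.175 at 270; 4 million simulated runs), power is 88.3%. The stopping probabilities under no effect are 0.497 and 0.346, as tabulated. The design figures reproduce, and they do not depend on the choice of clock.

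**2. Simulating the clock.** Inputs from the plan: 350 per arm, control median 15 days, whole-day times, Day 29 horizon, deaths kept at risk to Day 29 as 16.1.1 prescribes, and 15% mortality (Master SAP 7.1, applied here to both arms). Assumptions, because the documents give nothing: the share of one arm dosed a day late, and the shape k of the recovery hazard, with cumulative hazard ln 2 × (t/15)^k for k = 1, 1.5 and 2. Observed time = recovery day − delay + 1; patients who recover before dosing count as never dosed. The test is an unstratified log-rank with rejection at z > 1.96 and no futility stopping, 2,000 runs per case, true hazard ratio 1.

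| Net share of one arm dosed one day later | Hazard ratio (k = 1 / 1.5 / 2) | One-sided error in favour of the later-dosed arm |
|---|---|---|
| 0% | 1.001 / 0.999 / 0.999 | 3.0 / 2.5 / 3.0% |
| 10% | 1.006 / 1.004 / 1.005 | 2.7 / 2.5 / 3.6% |
| 25% | 1.013 / 1.016 / 1.020 | 3.3 / 3.2 / 4.5% |
| 50% | 1.023 / 1.033 / 1.036 | 4.5 / 6.0 / 5.9% |
| 100% | 1.046 / 1.062 / 1.071 | 7.7 / 10.8 / 13.1% |
| 100%, clock at randomization | 1.001 / 1.002 / 0.998 | 2.8 / 2.7 / 2.5% |

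Monte Carlo standard error near 2.5% is √(0.025 × 0.975/2000) = 0.35 percentage points, so the 10% row is barely distinguishable from no delay.

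**3. The opposite direction.** With a true ratio of 1.364 and the one-day delay in 25% of control instead (1,000 runs), the estimate falls from 1.285 to 1.268 (k = 1), 1.253 to 1.229 (k = 1.5) and 1.204 to 1.183 (k = 2). The no-delay values lie below 1.364 because patients who die remain at risk to Day 29 in this model; only the change is relevant here.

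**4. From product delay to net difference.** The agent's own placebo is in control. If placebo patients split equally among m open agents for which all qualify, and the agent's product is dosed late in a fraction f against g for the others, the net difference is f − [f/m + (1 − 1/m)g] = (1 − 1/m)(f − g). With f = 30% and g = 0 this is 15% for m = 2 and 20% for m = 3, between the 10% and 25% rows.

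**The case against.** The strongest reply is that the planned gap is zero. The schedules put both events on Day 1, the SAP follows the protocol's own day numbering, and in whole days a pharmacy delay of some hours changes nothing. Control patients come only from sites where the agent's sub-protocol is open, so site workflow is largely shared, and the agent's own placebo follows the same route and schedule. All of this stands, and it makes the point conditional. It does not show that the two dates always coincide: no interval is enforced, and 6.1 itself handles them as separate dates.

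Direction is also open. The lanadelumab and zilucoplan SAPs drop efficacy inference, so among the sub-protocol SAPs supplied only apremilast keeps the test. Apremilast is oral; if infusions or injections were started later than tablets, the pooled control would be the later-dosed arm and the bias would run against apremilast.

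A reader might take the early termination of lanadelumab over administration problems (COV-01-001 SAP 3.3) as evidence of dosing delay. That section says nothing about time to first dose, and no efficacy test remains there. A reader might also infer that a randomized comparison is valid only with a randomization origin. That goes too far, since equal delays leave it unbiased.

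Finally, delay may be partly visible already. Dose dates and times are collected (Protocol 6.4), and Master SAP 9.2 tabulates critical and major deviations by arm, with control split by sub-protocol. Whether late dosing counts as such is set in a plan not supplied.

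**Conclusion.** The point holds as a conditional weakness in the definition of the primary clock. One as-randomized comparison carries two time origins, one fixed after randomization, and no planned analysis tests whether that matters. The size depends entirely on a net between-arm difference in next-day dosing, which the documents neither report nor bound. If it is about 10%, the effect is negligible (hazard ratio 1.00 to 1.01). At 25% it is small but reaches the error rate (1.01 to 1.02; 3.2% to 4.5% against 2.5%). Only a systematic shift of about a day across an arm would matter greatly, and nothing in the documents suggests one. They do not support a claim that the plan is biased in the agent's favour. Because the origin sits in the Master SAP, it applies to every agent tested under it. This is a cheap improvement, not a defect that invalidates the comparison.

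**What to change.** In Master SAP 16.1.1, and in the time-to-death analyses of 16.2.5 and 16.4.5, use the randomization date as time zero for every patient in the full analysis set. At minimum, pre-specify that version as a sensitivity analysis in 16.1.4. Keep first dose as Day 1 for safety, exposure, baseline and the endpoints read at scheduled visits, all of which are anchored to it. Tabulate time from randomization to first dose by arm and by placebo sub-protocol.

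The cost is a second day count in the programs. For a patient dosed one day late, the Day 29 horizon and the scheduled Day 29 visit would differ by one day, inside the visit's ±3-day window. The response system that randomizes already holds the date, patients dosed on the day of randomization are unaffected, and the planned 490 events and 88.3% power do not change.
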